7.2 Minimizing Study Risks56
7.3 Benefit-Risk Summary57
7.4 Anticipated Changes during the Investigation59
8.0 MONITORING PLAN60
9.0 REFERENCES61
APPENDIX A: DEFINITIONS66

List of Tables

Table 1 Abbreviations12
Table 2 Calypso Knee System Implant Components.....23
Table 3 Imaging Assessment Schedule32
Table 4 Calypso Knee System Clinical Study Schedule of Events.....37

Calypso Knee System Clinical Study

PROTOCOL SUMMARY

Protocol Title:	Evaluation of the Calypso Knee System for Symptom Relief in Subjects with Medial Knee Osteoarthritis Short Title: Calypso Knee System Clinical Study
Protocol Number:	CP0001 (formerly CLIN102837)
Study Objective:	A pivotal study to evaluate the safety and effectiveness of the Calypso Knee System when used in subjects with symptomatic osteoarthritis of the medial compartment of the knee.
Study Design:	Prospective, multicenter clinical study comparing the Calypso Knee System to the cohort of subjects treated with High Tibial Osteotomy (HTO) from a recent non-randomized trial (GOAL study).
Intended Use:	The Calypso Knee System is intended to treat symptoms of pain and loss of knee function in subjects with a diagnosis of osteoarthritis in the medial compartment of the knee.
Device Description:	

Calypso Knee System Clinical Study

Staged Enrollment:
	
[REDACTED]

Sample Size and Number of Sites:
	
80 subjects will be enrolled in this study at up to 10 investigational sites located in the U.S.

Patient Population:
	
Male or female subjects age 25 to 65 years, with a diagnosis of medial knee osteoarthritis and study knee pain with an overall WOMAC pain score ≥ 40 (scale 0-100).


Inclusion/Exclusion Criteria:
	
Radiographic criteria (Inclusion #6 and Exclusion #3, 4, 5) will be assessed by an independent core laboratory per the Radiographic Evaluation Protocol (CLIN102792) as part of the screening process.
 
Inclusion Criteria Subjects enrolled in the study must meet all of the following criteria:
 
 1. Subjects age 25 to 65 years at time of screening 2. Body Mass Index (BMI) of < 35 3. Weight < 300 lbs 4. WOMAC pain ≥ 40 5. Knee flexion $\geq 90^\circ$ and $\leq 140^\circ$ 6. Clinical symptoms (such as pain primarily localized to the medial aspect of the study knee and generally exacerbated by weight bearing) and radiographic evidence, using a weight-bearing fixed flexion view, of osteoarthritis in the study knee as defined as KL grade of 1-4* 7. Failed at least 6 months of non-operative treatment defined as at least one of the treatments per AAOS Treatment of Osteoarthritis of the Knee; Evidence based guideline 2nd Edition 2013 
Exclusion Criteria Subjects will be excluded from the study if any of the following conditions apply:
 
Knee Osteoarthritis
 
 1. Radiographic evidence of large, defined as $> \text{Grade } 2^+$, marginal osteophytes in the medial compartment of the study knee 2. Bony erosion 3. Clinical symptoms or radiographic evidence of osteoarthritis in the: 
 a. Lateral compartment of the study knee defined as KL grade of $> 2^*$ b. Patellofemoral compartment of the study knee defined as KL grade $> 3^*$ 4. Clinical symptoms or radiographic evidence of osteoarthritis at the contralateral knee that would preclude activity of daily living, stair climbing, stair descending,

Calypso Knee System Clinical Study

	
or requires the use of an assist device*
 
5. Mechanical axis alignment (Hip-Knee-Ankle) < -16° (varus) or > 0° (valgus) OR anatomic axis alignment < -10° (varus) or > 6° (valgus) as measured on a Long Standing AP X-ray view*6. Hyperextension > 5°7. Flexion contracture > 10°8. Insufficiency of the cruciate and collateral ligaments, which would preclude stability of the Calypso Knee System9. Pathologic ligamentous (Lachman > 1) or meniscal instability10. Previous knee surgeries:
a. Lateral meniscectomy, patellar surgery, osteotomy, prior knee implant, or knee joint replacement of the study kneeb. Joint modifying surgery in the study knee within 12 months of index procedure (e.g., ligament reconstruction, meniscus repair, cartilage transplantation, microfracture, etc.)c. Arthroscopic surgeries in the study knee within 3 months of index procedure for joint lavage, meniscectomy, chondral debridement, and loose body removal 
Joint or Bone Complications/Comorbidities
 
11. Active infection, sepsis, osteomyelitis or history of septic arthritis in any joint12. Rheumatoid arthritis, other forms of inflammatory joint disease or autoimmune disorder13. Paget's disease or metabolic disorders which may impair bone formation14. Osteomalacia or osteonecrosis (known or suspected)15. Known or suspected rapidly destructive OA (RDO) as determined by the investigator⁺⁺16. Charcot's joint disease17. Osteoporosis Self-Assessment Tool (OST) score of < 4 for women or < 6 for men AND a T-score less than -1.0 based on a DEXA scan of the proximal femur (preferred) or lumbar spine. All subjects with an OST score < 4 for women or < 6 for men will undergo a DEXA scan to determine the bone mineral density T-score.18. Steroid treatment (oral or IV), medication use that affects bone metabolism (such as chemotherapy) or radiotherapy within 6 months of index procedure19. Bone malignancy (active or history) 
Other Complications/Comorbidities
 
20. Allergy or hypersensitivity to cobalt, chromium, iron, or nickel metals (suspected or documented)21. Life expectancy estimated to be less than 5 years (i.e., malignancies, end stage liver, kidney, cardiac failure)22. Co-morbidities that could impact study participation or results:
a. Neurological disorders affecting gaitb. Neuropathic pain or fibromyalgia, restless leg syndrome, complex regional pain syndrome or Reflex Sympathetic Dystrophy (RSD) or pain requiring
--	--

Calypso Knee System Clinical Study

	
chronic pain management
 
c. Severe neurosensory deficits, muscular atrophy, neuromuscular disease
 
d. Immunologically suppressed or immunocompromised patients such as HIV
 
e. Diabetes mellitus requiring daily insulin therapy
 
f. Radicular symptoms associated with lumbar spine pathology
 
g. Significant psychiatric disorders (e.g., major depression, anxiety disorders, bipolar disorder, and schizophrenia)
 
h. Substance and alcohol dependence and abuse (meeting standard diagnostic criteria described in the Diagnostic and Statistical Manual of Mental Disorders DSM-V)
 
General Conditions
 
23. Pregnancy or planning to become pregnant
 
24. Subjects unable to give voluntary written informed consent to participate
 
25. Subjects who are currently involved in any investigational drug or device trial or have been enrolled in such trials within 3 months of index procedure
 
26. Other factors that the investigator feels would interfere with the participation and completion of the study such as:
 
a. Unable to understand the clinical investigation or cooperate with investigational procedures
 
b. Planned relocation or unable to return for required follow-up visits
 
c. Active litigation for musculoskeletal injuries or disorders
 
d. Active workers compensation or Labor & Industries claim for musculoskeletal injury or disorder
 
*Radiographic analysis will be provided by an independent imaging core laboratory to support the investigator in confirming inclusion/exclusion criteria prior to enrollment.
 
⁺Altman RD, Gold GE Atlas of individual radiographic features in osteoarthritis, revised. Osteoarthritis Cartilage. 2007;15 Suppl A:A1-56 (pg. 42-49).
 


Primary Endpoint:
	
24 month composite endpoint demonstrating non-inferiority of the Calypso Knee System to HTO data. A subject is a responder if all of the following components are met at 24 months:
 
 • Clinically significant improvement of at least 20% from baseline on the WOMAC pain questions in the KOOS Knee questionnaire with a change of ≥ 10 points • Clinically significant improvement of at least 20% from baseline on the WOMAC function questions in the KOOS Knee questionnaire with a change of ≥ 10 points • Freedom from the following device-related serious adverse events: 
 ○ deep infection requiring surgical intervention (Both arms) ○ damage to adjacent neurovascular or ligament structures necessitating reconstruction (Both arms) ○ non-union (HTO only) • Maintenance of implant integrity as evaluated by radiographic assessment 
NOTE: A subject will be considered a non-responder if they have a conversion to

Calypso Knee System Clinical Study

	arthroplasty or loss of implant integrity of the Calypso Knee System at 24 months.
Secondary Endpoints:	
Secondary endpoints demonstrating superiority of the Calypso Knee System to HTO data for each of the following:
 
Recovery:
 
 1. Time to full weight bearing 
Early WOMAC Pain and Function:
 
 2. Percent change from baseline to 3 months on the WOMAC pain in the Knee injury and Osteoarthritis Outcome Score (KOOS Knee Survey) 3. Percent change from baseline to 3 months on the WOMAC function in the Knee injury and Osteoarthritis Outcome Score (KOOS Knee Survey) 
Durability of WOMAC Pain and Function:
 
 4. Percent change from baseline to 24 months on the WOMAC pain in the Knee injury and Osteoarthritis Outcome Score (KOOS Knee Survey) 5. Percent change from baseline to 24 months on the WOMAC function in the Knee injury and Osteoarthritis Outcome Score (KOOS Knee Survey)
Additional Observations:	
Safety Observations:
 
 • Knee Range of Motion (ROM) 
 ○ Measured passively defined as degrees of flexion and extension • Adverse Events by type, over time, severity, seriousness, and relatedness • Secondary surgical interventions by type of surgical intervention (revision, removal, re-operation (includes conversion to arthroplasty) supplemental fixation, other intervention) • Metal ion levels • In the event of a Calypso Knee System removal, the following assessments will be evaluated: 
 ○ Radiographic evaluations ○ MRI assessment as available ○ Calypso Knee System (implant) retrieval analysis ○ Histology ○ Metal Ion levels ○ Arthroplasty conversion data, if applicable 
Effectiveness/Other Observations:
 
 • Patient reported knee outcome measures and activity (KOOS Knee Survey, KSS, Subject Activity and Satisfaction, SF-12 Health Survey) • Investigator reported KSS
Statistical Analyses:	
Primary Statistical Analysis
 
The primary objective is to establish that the Calypso Knee System is non-inferior to HTO on a responder analysis combining pain, function, specified device-related SAEs, and implant integrity. A subject is considered a responder if he/she meets all success criteria that comprise the definition of the composite end-point at 24 months.
 
Secondary Statistical Analysis
 
Secondary Statistical Analysis will only be conducted upon a successful primary analysis of non-inferiority. Analysis of secondary objectives will take a hierarchical

Calyпсо Knee System Clinical Study

	
approach. These analyses will be conducted sequentially, starting from the first objective with progression towards the fifth objective. Each subsequent objective is only analyzed when all of the previous analyses are successful at demonstrating superiority.
 
Additional Observations Analysis
 
Traditional confidence intervals and p-values will be reported for these analyses, as applicable.
 
 • Knee Range of Motion (ROM) – evaluation using Calypso Knee System at baseline compared to 24 months • Adverse Events by type over time, severity, seriousness, and relatedness. AEs will be tabulated and summarized as counts and percentages. AEs will also be cross-tabulated according to: 
 ○ Severity; ○ Unanticipated Adverse Device Effect (UADE) ○ Seriousness (Serious Adverse Event (SAE), Non-serious AE); ○ Device-Relatedness (Unrelated, Possibly Related, Probably Related, Definitely Related); ○ Procedure-Relatedness (Unrelated, Possibly Related, Probably Related, Definitely Related). • Secondary surgical interventions by type of surgical intervention (revision, removal, re-operation (includes conversion to arthroplasty) supplemental fixation, other intervention) • Changes in patient reported knee outcome measures and activity (KOOS Knee Survey, KSS, Subject Activity and Satisfaction, SF-12 Health Survey) as compared to baseline • Changes in Investigator reported KSS
Study Duration:	All subjects included in this study will return for follow-up visits at 6 weeks and 3, 6, 12, 18, and 24 months, then annually through 5 years.
References:	
CLIN102840: Calypso Knee System Metal Ion Protocol LBL102812: Calypso Knee System, Instructions for Use - Product Insert LBL102811: Calypso Knee System Instruments, Instructions for Use - Product Insert CLIN102845: Calypso Knee System Surgical Technique Guide CLIN102792: Calypso Clinical Study Radiographic Evaluation Protocol CLIN102799: Calypso Clinical Study Informed Consent CLIN102852: Calypso Clinical Study Implant Retrieval Protocol CLIN102838: Calypso Knee System Rehabilitation Guideline CLIN102842: Calypso Clinical Study Investigator’s Agreement CLIN103113: Statistical Considerations and Preliminary Propensity Score (PS) Design Memorandum CLIN102839: Calypso Clinical Study Surgeon Training CLIN102853: Calypso Clinical Study Monitoring Plan CLIN102859: Calypso Clinical Study CEC Charter

Calypso Knee System Clinical Study

1.0 STUDY PURPOSE

1.1 Introduction and Background

[REDACTED]

[REDACTED]

[REDACTED]

Calypso Knee System Clinical Study

Load Bearing and Joint Mechanics

[REDACTED]

[REDACTED]

[REDACTED]

[REDACTED]

1.1.1 Current Conservative Care

[REDACTED]

[REDACTED]

Calypso Knee System Clinical Study

[REDACTED]

[REDACTED]

1.1.2 Education

[REDACTED]

1.1.3 Weight loss

[REDACTED]

1.1.4 Exercise

[REDACTED]

1.1.5 Physical Therapy

[REDACTED]

Calypso Knee System Clinical Study

1.1.6 Knee Braces and Orthotics

[Redacted text block]

1.1.7 Pharmacologic Approaches

[Redacted text block]

[Redacted text block]

[Redacted text block]

1.1.8 Current Surgical Treatment Options

[Redacted text block]

Calypso Knee System Clinical Study

[REDACTED]

High Tibial Osteotomy

[REDACTED]

[REDACTED]

[REDACTED]

Calypso Knee System Clinical Study

Joint Unloading with External Joint Distraction

[Redacted text block]

[Redacted text block]

[Redacted text block]

Knee Arthroplasty

[Redacted text block]

[Redacted text block]

Calypso Knee System Clinical Study

[Redacted]

1.1.9 Conclusions

[Redacted]

[Redacted]

1.2 Rationale for This Study

[Redacted]

[Redacted]

[Redacted]

Calypso Knee System Clinical Study

[REDACTED]

[REDACTED]

[REDACTED]

[REDACTED]

[REDACTED]

1.3 Device Name

For purposes of this study, “investigational device” or “study device” refers to the Calypso Knee System.

1.4 Description of the Device

[figure not shown]
[figure not shown]
[figure not shown]

Figure 2. Calypso Knee System with cross-section of Absorber on the right

Calypso Knee System Clinical Study

[REDACTED]

1.4.1 Mechanism of Action

[REDACTED]

[figure not shown]
[REDACTED]

[REDACTED]

[REDACTED]

The components of the Calypso Knee System are described in Table 2 below.

[figure not shown]
Table 2 Calypso Knee System Implant Components

1.5 Intended Use Statement

The Calypso Knee System is intended to treat symptoms of pain and loss of knee function in subjects with a diagnosis of osteoarthritis in the medial compartment of the knee.

1.6 Prior Clinical Investigation

Calypso Knee System Clinical Study

[REDACTED]

[REDACTED]

2.0 PROTOCOL

2.1 Study Objective

The Calypso Clinical study is a pivotal study to evaluate the safety and effectiveness of the Calypso Knee System when used in subjects with symptomatic osteoarthritis of the medial compartment of the knee.

2.1.1 Study Design Overview

The Calypso Clinical Study is a prospective, multicenter clinical study comparing the Calypso Knee System to the cohort of subjects treated with High Tibial Osteotomy (HTO) from a recent non-randomized trial (GOAL study). A total of 80 subjects will be enrolled in this study at up to 10 investigational sites located in the U.S. using a staged enrollment.

[REDACTED]

The subject population for this study is male or female subjects age 25 to 65 years, with a diagnosis of medial knee osteoarthritis and study knee pain with an overall WOMAC pain score ≥ 40 (scale 0-100).

All subjects included in this study will return for follow-up visits at 6 weeks and 3, 6, 12, 18, and 24 months, then annually through 5 years.

At each follow-up visit, safety and effectiveness data will be collected. Subjects will be interviewed to determine if adverse events (AEs) were experienced since the previous follow-up visit. A complete orthopaedic knee assessment will be performed at baseline for all subjects and again during each follow-up visit. All subjects will be required to complete the KOOS Knee Survey and KSS to evaluate function, pain, and quality of life at each follow-up visit.

Calypso Knee System Clinical Study

Radiographic evaluations will be performed at pre-op, prior to discharge, 6 weeks, 3 months, 6 months, 12 months, 18 months, 24 months and annually thereafter through 5 years for all subjects. Radiographic evaluations will also be performed within 60 days prior to any planned Calypso Knee System removal.

MRI evaluations will be performed at the pre-procedure and at 2 and 5 year follow-up visits.

2.2 Study Scope and Participating Institutions

[REDACTED]

2.3 Patient Population

[REDACTED]

[REDACTED]

[REDACTED]

[REDACTED]

2.3.1 Inclusion/Exclusion Criteria

Radiographic criteria (Inclusion #6 and Exclusion #3, 4, 5) will be assessed by an independent core laboratory per the Radiographic Evaluation Protocol (CLIN102792) as part of the screening process.

Inclusion Criteria

Subjects enrolled in the study must meet all of the following criteria:

1. Subjects age 25 to 65 years at time of screening
2. Body Mass Index (BMI) of < 35
3. Weight < 300 lbs

Calypso Knee System Clinical Study

4. WOMAC pain ≥ 40
5. Knee flexion $\geq 90^\circ$ and $\leq 140^\circ$
6. Clinical symptoms (such as pain primarily localized to the medial aspect of the study knee and generally exacerbated by weight bearing) and radiographic evidence, using a weight-bearing fixed flexion view, of osteoarthritis in the study knee as defined as KL grade of 1-4*
7. Failed at least 6 months of non-operative treatment defined as at least one of the treatments per *AAOS Treatment of Osteoarthritis of the Knee; Evidence based guideline 2nd Edition 2013*

Exclusion Criteria

Subjects will be excluded from the study if any of the following conditions apply:

Knee Osteoarthritis

1. Radiographic evidence of large, defined as $> \text{Grade } 2^+$, marginal osteophytes in the medial compartment of the study knee
2. Bony erosion
3. Clinical symptoms or radiographic evidence of osteoarthritis in the:
 - a. Lateral compartment of the study knee defined as KL grade of $>2^*$
 - b. Patellofemoral compartment of the study knee defined as KL grade $> 3^*$
4. Clinical symptoms or radiographic evidence of osteoarthritis at the contralateral knee that would preclude activity of daily living, stair climbing, stair descending, or requires the use of an assist device*
5. Mechanical axis alignment (Hip-Knee-Ankle) $< -16^\circ$ (varus) or $> 0^\circ$ (valgus) OR anatomic axis alignment $< -10^\circ$ (varus) or $> 6^\circ$ (valgus) as measured on a Long Standing AP X-ray view*
6. Hyperextension $> 5^\circ$
7. Flexion contracture $> 10^\circ$
8. Insufficiency of the cruciate and collateral ligaments, which would preclude stability of the Calypso Knee System
9. Pathologic ligamentous (Lachman > 1) or meniscal instability
10. Previous knee surgeries:
 - a. Lateral meniscectomy, patellar surgery, osteotomy, prior knee implant, or knee joint replacement of the study knee
 - b. Joint modifying surgery in the study knee within 12 months of index procedure (e.g., ligament reconstruction, meniscus repair, cartilage transplantation, microfracture, etc.)
 - c. Arthroscopic surgeries in the study knee within 3 months of index procedure for joint lavage, meniscectomy, chondral debridement, and loose body removal

Joint or Bone Complications/Comorbidities

11. Active infection, sepsis, osteomyelitis or history of septic arthritis in any joint
12. Rheumatoid arthritis, other forms of inflammatory joint disease or autoimmune disorder
13. Paget's disease or metabolic disorders which may impair bone formation
14. Osteomalacia or osteonecrosis (known or suspected)
15. Known or suspected rapidly destructive OA (RDO) as determined by the investigator⁺
16. Charcot's joint disease
17. Osteoporosis Self-Assessment Tool (OST) score of < 4 for women or < 6 for men AND a T-score less than -1.0 based on a DEXA scan of the proximal femur (preferred) or lumbar spine. All subjects with

Calypso Knee System Clinical Study

an OST score < 4 for women or < 6 for men will undergo a DEXA scan to determine the bone mineral density T-score.

18. Steroid treatment (oral or IV), medication use that affects bone metabolism (such as chemotherapy) or radiotherapy within 6 months of index procedure
19. Bone malignancy (active or history)

Other Complications/Comorbidities

20. Allergy or hypersensitivity to cobalt, chromium, iron, or nickel metals (suspected or documented)
21. Life expectancy estimated to be less than 5 years (i.e., malignancies, end stage liver, kidney, cardiac failure)
22. Co-morbidities that could impact study participation or results:
 - a. Neurological disorders affecting gait
 - b. Neuropathic pain or fibromyalgia, restless leg syndrome, complex regional pain syndrome or Reflex Sympathetic Dystrophy (RSD) or pain requiring chronic pain management
 - c. Severe neurosensory deficits, muscular atrophy, neuromuscular disease
 - d. Immunologically suppressed or immunocompromised patients such as HIV
 - e. Diabetes mellitus requiring daily insulin therapy
 - f. Radicular symptoms associated with lumbar spine pathology
 - g. Significant psychiatric disorders (e.g., major depression, anxiety disorders, bipolar disorder, and schizophrenia)
 - h. Substance and alcohol dependence and abuse (meeting standard diagnostic criteria described in the Diagnostic and Statistical Manual of Mental Disorders DSM-V)

General Conditions

23. Pregnancy or planning to become pregnant
24. Subjects unable to give voluntary written informed consent to participate
25. Subjects who are currently involved in any investigational drug or device trial or have been enrolled in such trials within 3 months of index procedure
26. Other factors that the investigator feels would interfere with the participation and completion of the study such as:
 - a. Unable to understand the clinical investigation or cooperate with investigational procedures
 - b. Planned relocation or unable to return for required follow-up visits
 - c. Active litigation for musculoskeletal injuries or disorders
 - d. Active workers compensation or Labor & Industries claim for musculoskeletal injury or disorder

*Radiographic analysis will be provided by an independent imaging core laboratory to support the investigator in confirming inclusion/exclusion criteria prior to enrollment.

⁺Altman RD, Gold GE Atlas of individual radiographic features in osteoarthritis, revised. Osteoarthritis Cartilage. 2007;15 Suppl A:A1-56 (pg. 42-49).

Calypso Knee System Clinical Study

2.4 Study Endpoints

2.4.1 Primary Endpoint

The primary endpoint is a 24 month composite endpoint demonstrating non-inferiority of the Calypso Knee System to HTO data. A subject is a responder if all of the following components are met at 24 months:

- Clinically significant improvement of at least 20% from baseline on the WOMAC pain questions in the KOOS Knee questionnaire with a change of ≥ 10 points
- Clinically significant improvement of at least 20% from baseline on the WOMAC function questions in the KOOS Knee questionnaire with a change of ≥ 10 points
- Freedom from the following device-related serious adverse events:
 - deep infection requiring surgical intervention (Both arms)
 - damage to adjacent neurovascular or ligament structures necessitating reconstruction (Both arms)
 - non-union (HTO only)
- Maintenance of implant integrity as evaluated by radiographic assessment

NOTE: A subject will be considered a non-responder if they have a conversion to arthroplasty or loss of implant integrity of the Calypso Knee System at 24 months

Details of the radiographic assessment for implant integrity may be found in the Radiographic Evaluation Protocol (CLIN102792).

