2.6 Study Duration

All subjects included in this study will return for follow up visits at 6 weeks, 3 months, 6 months, 12 months, 18 months and 24 months post index procedure. Evaluation of the primary endpoint will be completed on all subjects at 24 months post procedure. Follow-up visits will continue annually for a total of 5 years.

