4.3 Subsequent Surgical Interventions of the Knee

- **Revision:** A revision is a procedure that adjusts or in any way modifies or removes *part* of the original implant configuration with or without replacement of a component. A revision may also include adjusting the position of the original configuration. This may include removing a component of the device and only replacing that single component.
- **Removal:** A removal is a procedure where all of the original system configuration is removed with or without replacement due to, for example, mechanical failure of the device, pain or infection.
- **Re-operation:** A reoperation is any surgical procedure that does not include removal modification, or addition of any components to the system (e.g., drainage of a hematoma at the surgical site).
- **Supplemental fixation:** A supplemental fixation is a procedure in which additional instrumentation not under study in the protocol is implanted.
- **Other interventions:** This category includes other surgeries of the study knee that the subject incurs while enrolled in the study that seemingly are unrelated to the implanted device.

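### Section 2.4.1 does not say that revision, or removal with replacement, of the Calypso device before 24 months makes a subject a non-responder

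*Combined protocol and SAP*

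**What the plan says.** Section 2.4.1, repeated in the Protocol Summary, opens the responder rule with "A subject is a responder if all of the following components are met at 24 months". The components are:

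- improvement in WOMAC pain of at least 20% and at least 10 points;
- the same for WOMAC function;
- freedom from named device-related serious adverse events: deep infection needing surgery, neurovascular or ligament damage needing reconstruction, and non-union for HTO only;
- implant integrity maintained on radiographs.

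The NOTE then adds: "A subject will be considered a non-responder if they have a conversion to arthroplasty or loss of implant integrity of the Calypso Knee System". Its time qualifier appears in the Summary version: "arthroplasty or loss of implant integrity of the Calypso Knee System at 24 months". For the integrity component, 2.4.1 refers the reader elsewhere: "Details of the radiographic assessment for implant integrity may be found in the Radiographic Evaluation Protocol (CLIN102792". Section 5.0 refers the primary analysis to a separate memorandum, CLIN103113.

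Section 4.3 defines the later operations. On revision it says "A revision may also include adjusting the position of the original configuration", and it also covers "removing a component of the device and only replacing that single component". Removal means taking out the whole original system, whether or not it is replaced, and the example reasons are mechanical failure, pain and infection. Section 4.3 gives none of its categories a responder status. The Summary lists them as additional observations: "Secondary surgical interventions by type of surgical intervention (revision, removal, re-operation (includes conversion to arthroplasty) supplemental fixation, other intervention". Section 5.1 does the same. Section 5.3 keeps subjects in follow-up, with questionnaires, after removal.

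**The concern.** The composite is meant to show that the implanted device works. If a second operation repositions the device, exchanges a part or replaces the whole system, a good 24-month score reflects the index procedure plus that operation. On the wording of 2.4.1 it is still credited to the index device, in the one comparison that decides the trial. In a non-inferiority test, a rule that leaves device re-intervention unscored on the investigational side is lenient where the test should be strict. The comparator is a cohort from another, non-randomized trial, so the scoring rule also needs to be explicit enough to apply in the same way to both groups.

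**Working it through.** The plan gives no figure to reproduce. It states no re-intervention rate, and it does not give the non-inferiority margin or the HTO sample size. The check is therefore a trace of section 4.3 events through the 2.4.1 rule.

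**Case A: device repositioned, one component exchanged, or whole system removed and replaced, for pain, before 24 months.**
1. WOMAC pain and function: met, if the gains reach 20% and 10 points on each.
2. Listed serious adverse events: met, because pain is not on the list.
3. Integrity: met as worded, if the 24-month film shows intact hardware.
4. NOTE: not triggered, because there is no arthroplasty and no radiographic loss of integrity at any time.

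Result: responder. This does not depend on how the time qualifier is read.

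**Case B: integrity lost, corrected by revision, intact at 24 months.** If the qualifier means status at the visit, the subject passes. If it means through 24 months, the subject fails. Section 2.6 does not settle the matter: "Evaluation of the primary endpoint will be completed on all subjects at 24 months post procedure" says when the evaluation is done, not what period it covers.

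**Case C: removal without replacement.** There is no implant left to be judged intact, so failure on integrity is the most plausible reading, although 2.4.1 does not say so.

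**Case D: revision or removal for device-related deep infection needing surgery, or with listed structural damage needing reconstruction.** The subject already fails.

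**Case E: conversion to arthroplasty.** The subject already fails under the NOTE.

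The gap is therefore Case A, plus Case B on one of its two readings.

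**Size on the crude Calypso rate.** The input is 80 subjects (section 2.1.1), assuming that all are analysed. If k subjects in the gap are counted as responders, the rate is higher by k/80:

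| k (assumed) | k/80 | percentage points |
|---|---|---|
| 1 | 0.0125 | 1.25 |
| 2 | 0.025 | 2.5 |
| 4 | 0.05 | 5.0 |
| 8 | 0.10 | 10.0 |

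The documents give no basis for choosing k. Nor is k/80 the shift in the treatment comparison. That comparison rests on a propensity-score design held in CLIN103113, where a subject need not carry a weight of 1/80. Revision of an osteotomy or its fixation is not named as failure for HTO either, so HTO subjects could be credited in the same way.

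**The case against.** The strongest reply is that the rule may exist elsewhere. CLIN102792 may define integrity by the original configuration, so that a repositioned or exchanged device has not maintained it, and CLIN103113 may score re-intervention directly. Neither document is available here, and other parts of the protocol are redacted. This stands, and it limits the point to what 2.4.1 and the Summary say. It does not remove the point, because those two places carry the responder definition unredacted, and the pointer to CLIN102792 promises only details of the radiographic assessment.

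Second, a cumulative reading of the time qualifier is at least as natural. The same words govern infection and arthroplasty, which are naturally cumulative. Section 2.1.1 also schedules films at every visit and within 60 days before a planned removal. This weakens Case B but leaves Case A untouched.

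Third, the gap is narrow: infection, arthroplasty and probably most mechanical failures already fail, and the remaining subjects must still reach both WOMAC thresholds. This is fair, and it is why the size is stated per subject.

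A reader might also infer from section 5.1, which asks for arthroplasty data after removal only where it applies, that the plan expects removals to escape failure. It shows only that removal can occur without arthroplasty; such a removal may still count as loss of integrity.

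**Conclusion.** The point holds on the text. As worded, 2.4.1 and the Summary let a Calypso subject with a revision, or a removal with replacement, before 24 months count as a responder when the reason lies outside the listed events and integrity is judged intact. The wording also does not settle whether an earlier, corrected loss of integrity counts. The crude Calypso rate rises by 1.25 points per such subject, assuming 80 analysed.

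Three stronger conclusions might be drawn, and the documents support none of them:

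- That the non-inferiority comparison is biased by a known amount, or even in a known net direction. The number of events, the margin, the HTO sample size and the propensity-score method are not given, and HTO re-intervention is equally unnamed.
- That no study document scores these events, so the rule would have to be made after they are known. Two governing documents are unseen.
- That inconsistent labelling of arthroplasty changes who responds. Section 4.3 excludes removal of components from re-operation, while the Summary and 5.1 place conversion to arthroplasty under it. Conversion is failure under any label, so this is editorial only.

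**What to change.** Reword the NOTE in 2.4.1 and the Summary so that a subject is a non-responder if any of the following occurs between the index procedure and the 24-month visit, whether or not later corrected:

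- conversion to arthroplasty;
- radiographic loss of Calypso implant integrity;
- revision or removal of the Calypso system as section 4.3 defines them, whether or not a device is put back.

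Pre-specify a parallel rule for HTO, namely revision of the osteotomy or its fixation, where the GOAL records allow it. Where they do not, state that the comparison is stricter for Calypso. Report the current definition as a sensitivity analysis. If CLIN102792 or CLIN103113 already scores these events, state that rule in 2.4.1 instead. Separately, reconcile the re-operation label between 4.3, 5.1 and the Summary.

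The cost on the Calypso side is small: a reworded NOTE and alignment of the two referenced documents, since interventions are already to be reported by type. The crude Calypso rate would fall by 1.25 points for each responder reclassified. The HTO side needs a review of existing GOAL records, and the documents do not show whether those events can be classified.
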